10.0 CRITERIA FOR EVALUATION AND ENDPOINT DEFINITIONS

The primary outcome is arrest of interproximal caries on a primary molar, as measured by lack of change in ICCMS classification indicating caries progression on radiographic examination, (higher score indicates progression). The outcome will be evaluated at three time points: baseline, 6 months and 12 months. As the treatments cannot be made to appear similar to one another, neither the treating dentist or the patient/parent(s) will be blinded to treatment status. However, evaluation of the outcome will made by comparing time lapse (ie. comparing intial xrays vs. at 6 months vs. at 1 year) bitewing radiographs and visualizing if the carious lesion has remineralized, arrested, or progressed

11.0 SPECIAL INSTRUCTIONS:

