13.0 STATISTICAL CONSIDERATIONS

- 13.1 The proposed pilot Phase III randomized controlled clinical trial aims to determine which of the following treatments is superior in arresting dental caries among patients presenting with interproximal caries scoring RA1 RA3 on the International Caries Classification and Management System (ICCMS): (1) Fluoride varnish (FV, current standard of care, control), (2) Super floss + SDF + FV, (3) SDF + FV. We hypothesize that group 2 will have the best outcomes, as measured by no change or reversal in ICCMS classification indicating no caries progression or remineralization on radiographic examination, (higher score indicates progression) followed by group 3. As we could find no data on ICCMS-defined progression or remineralization rates for either Super Floss or fluoride, we were unable to calculate power. Instead, we provide estimates of recruitment based on feasibility. We expect to accrue approximately 20 participants, with 2 qualifying teeth per participant, in each group.
- 10% loss to follow up has increased dramatically to ~48%. Given this unexpected setback, we now need to continue recruiting participants to reach sufficient power. We originally planned to enroll 39 subjects in the study, but would now like to add 21 new participants for a total of 60 participants.

Descriptive statistics will be calculated for all demographic and clinical characteristics to assess the degree to which randomization was successful using means and standard deviations or medians and interquartile ranges for continuous variables and counts and percentages for categorical variables.

The primary analysis will be by intent-to-treat. The primary outcome is the change in ICCMS category, as assessed by radiographic evidence, from baseline to 12 months, with a planned interim analysis to evaluate the endpoint at 6 months for early indications of efficacy. We will calculate the median difference at each time point and use an individual-level model with an adjustment to the standard error to account for the clustering. First we will evaluate the association between treatment groups and the change in ICCMS score from baseline at 6 and 12 months using a cluster-adjusted chi-squared test. We will further assess

14

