the relationship between these two variables using generalized estimating equations, specifying a Poisson (or negative binomial, if overdispersed) family and a log link. We will also specify an exchangeable correlation matrix and a robust standard error.

Since the study is randomized, we do not anticipate needing to adjust for any confounders. However, should we find any differences in demographic or clinical variables at baseline, we will investigate them as potential confounders, which will be defined as those variables which alter the odds ratio by >15% when included in the model.

For those with missing data on outcomes or other covariates to be included in the model, we will consider multiple imputation methods if the amount of missing data is <10%. To assess the impact of missing data, we will compare those with missing data to those not missing data with respect to demographic and clinical variables to assess comparability. Should imputation be utilized, a sensitivity analysis will be conducted excluding those for whom data was imputed to assess the impact of imputation.

Model fit will be evaluated by inspection of residuals and influential points. As we are conducting an interim analysis, we will use a two-sided Bonferroni-corrected p-value of a=.025 for statistical significance. Finally, to assess the degree to which the two raters agree with respect to classifying the outcome of the x-rays, we will calculate and report Kappa. All statistical analyses will be done using Stata 15.0 (College Station, TX).

Power Analysis

We calculated power using a cluster-randomized design. We were unable to locate any previous studies examining the impact of these three treatments (or any two) using the same classification system as our outcome. However, we were able to obtain an estimate of 0.0 to 0.25 for the interclass correlation coefficient (ICC) (Honkala et al., 2011). Assuming the mean ICC, and assuming a clinically significant mean difference of 0.2, a standard deviation of 0.2, a covariance of cluster sizes of 0.65, two caries on average per child, and a two-sided adjusted Type I error rate of 0.025 to account for the three time points at which the data will be analyzed, we will have 80% power with 11-12 participants per group, for a total of 33-36 participants (66-72 caries). Since we anticipate significant loss-to-follow-up over the course

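### The first planned test of the primary outcome ignores the order of the ICCMS change score; with four or more change values it is sparse, mostly conservative and about 10-30 points less powerful

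*Combined protocol and SAP*

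**What the plan says.** Section 13.1 defines the outcome as a change score: "The primary outcome is the change in ICCMS category, as assessed by radiographic evidence, from baseline to 12 months". It gives the direction of the scale ("higher score indicates progression") and counts both no change and reversal as favourable. The first analysis relates treatment arm to "the change in ICCMS score from baseline at 6 and 12 months using a cluster-adjusted chi-squared test". On significance it says "we will use a two-sided Bonferroni-corrected p-value of a=.025 for statistical significance". A GEE with a Poisson or negative binomial family and a log link follows.

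Section 10.0 words the outcome differently: "The primary outcome is arrest of interproximal caries on a primary molar, as measured by lack of change in ICCMS classification". That reads as binary. The same section then has readers compare films by "visualizing if the carious lesion has remineralized, arrested, or progressed", which has three levels.

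The Power Analysis assumes a mean difference of 0.2, an SD of 0.2, the midpoint of an ICC range of 0.0 to 0.25, a cluster-size variation of 0.65 and two lesions per child. It arrives at 11-12 children per group, 66-72 lesions in all. Recruitment is then raised to 54-60 children (108-120 lesions) to allow for about 48% loss. Under section 3.5, data already collected on children who drop out are discarded.

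**The concern.** Lesions enter at RA1 to RA3 on a 0-6 scale, so the change can take several negative and positive values. A chi-squared test of arm by change value treats these as unlabelled categories. With three arms and k values it spends 2(k - 1) degrees of freedom on about 20-24 lesions per arm, so its large-sample reference distribution is doubtful. It also ignores the fact that a two-step worsening is worse than a one-step worsening. The stake is efficiency. In a trial losing about half its children, the test that is run first on the primary outcome, at both looks, may operate well below its stated level and miss a difference that an ordered test would detect.

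**Working it through.** **1. The plan's own sample size.** The normal approximation for two means gives 2 × ((2.2414 + 0.8416) × 0.2/0.2)² = 19.01 lesions per arm. Reading the 0.65 as a coefficient of variation, the design effect is 1 + ((1 + 0.65²) × 2 - 1) × 0.125 = 1.2306. Then 19.01 × 1.2306 = 23.4 lesions, or 11.7 children per arm. The stated 11-12 is reproduced, but by a formula for a difference in means. The 80% does not describe a chi-squared test.

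**2. Analysable lesions per arm.** From the Power Analysis: 66/3 = 22 to 72/3 = 24. From recruitment less loss: 60 × 0.52 / 3 × 2 = 20.8. Enrolled: 108/3 = 36 to 120/3 = 40.

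**3. Sparseness.** A change value held by a fraction p of lesions has expected count 24p per arm with 24 lesions. This is below 5 whenever p < 5/24 = 20.8%. If most lesions are unchanged, nearly every other value falls below that line.

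**4. Level and power.** The documents give no response distribution and name no cluster correction, so both were assumed and varied. All runs have three arms and, except where stated, 10-12 children per arm.
- Fixed design effect: two lesions per child, ICC 0 or 0.125, Pearson chi-squared divided by the matching design effect (1 or 1.125), 60,000 null and 40,000 power trials. The comparator is a mean-score test with the same adjustment.
- Rao-Scott: cluster sizes 1-6 (mean 2.02, CV 0.66), ICC 0.125, second-order F or first-order correction, 600-4,000 runs. The comparator is a child-level permutation test of mean change. Its power figures are at 12 children per arm.
- Binary Rao-Scott runs: mean 2.04 lesions, CV 0.64, ICC 0.125, 4,000 null and 1,000 power runs.

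| Change tabulated as | Expected counts <5 | Level at nominal 2.5% | Power: chi-squared vs comparator |
|---|---|---|---|
| Five or seven values, fixed design effect | 67-81% | 0.25-0.66% (85-88% unchanged); 0.9-1.6% (55-70% unchanged) | Five values: 13-19% vs 31-39%; 41-54% vs 71-81% |
| Four or five values, Rao-Scott | 71-78% | second-order 0.3-0.7%; first-order 1.4-2.6% | second / first order 22% / 35% vs 51%; 8% / 17% vs 28% |
| Three values | 51-67% | fixed design effect 0.7-2.0%; second-order 1.4-2.4%; first-order 3.2% | 37-47% vs 49-59%; second / first order 23% / 32% vs 33% |
| Binary | 2-9% (70/30 split); about 50% (90/10) | fixed design effect 1.6-2.5%; first-order 1.2-2.4%; second-order 0.2-1.5% | first-order 55% vs 57%; second-order 47% vs 57% |

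One four-value distribution (10/60/25/5, 12 children per arm) gave 54% sparse cells and a level of 1.65%, so the degree of sparseness depends on the distribution. With 12 children per arm and ICC 0.125, separate runs gave power of 12% vs 30% (five values), 19% vs 28% (three values) and 54% vs 51% (binary).

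The comparators also differ. The permutation test kept a level of 2.3-2.6%. The mean-score test gave 0.9-1.7% with 85-88% of lesions unchanged and 1.85-2.2% with 55-70% unchanged.

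**5. The trial as it would run.** With 60 children in blocks of six, 48% loss, five values and 65% unchanged, the null rejection rate was 1.3% for chi-squared and 2.4% for permutation within blocks (1,500 runs). With arm means 0.59/0.24/-0.10, power was 20% vs 42% (800 runs).

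**6. Two boundary cases.** An SD of 0.2 implies that only about 4% of lesions move one step (0.2² = 0.04). Both tests are then conservative: 0.1-1.1% for chi-squared and 0.2-1.1% for the mean-score test. If lesions only stay or progress one step (20/10/0% by arm), the two tests have identical power, 19-27%. Separately, applying 1.2306 to equal pairs, where 1.125 is the matching value, pushes the five- and seven-value level down to 0.06-0.7%. That is over-correction and is left out of the ranges quoted.

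**The case against.** The strongest reply is that the multi-valued table is only one reading. Section 10.0 supports a binary or three-level outcome, and section 13.1 judges confounding by a change in the odds ratio, which suits a binary outcome. Under that reading with a first-order correction, the test behaves acceptably. This stands, and it limits the point. Even so, section 13.1 names the change score as what is tested and fixes no categories, so the plan does not secure the benign case.

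A reader might infer that the true level is 0.3-0.7%. The documents do not support that as a fact. It is a low end that needs four or more values together with either a second-order correction, which the plan does not name, or a distribution with about 85-88% of lesions unchanged.

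A reader might also infer that the trial's conclusion hangs on this test. No section makes it a gatekeeper; the text gives only its order. Median differences, an individual-level model and a GEE are also planned. The GEE does not make good the loss as written, however, because a Poisson or negative binomial family cannot take the negative changes that represent remineralisation.

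It is fair to add that a permutation test on between-arm variation is also unsigned. Its gain comes from using the score numerically. In both tests the direction is read from the estimates.

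**Conclusion.** The point holds, conditionally on how the change score is tabulated.
- **Four or more values:** most expected counts are below 5, the level is roughly 0.3-2.6%, and power is about 10-30 points lower than that of an ordered or permutation test.
- **Three values:** the level is about 0.7-3.2%, and the power loss ranges from about none to 12 points.
- **Binary arrest, first-order correction:** the level is about 1.2-2.5%, with little or no power loss.

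These figures rest on assumed response distributions, an ICC of 0 or 0.125, about two lesions per child and 10-12 analysable children per arm. At 20 children per arm, with no loss and a matching design effect, the five- and seven-value level was still 0.4-1.9%.

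The error is mainly conservative. A reader might infer an inflated false-positive risk, but apart from the 3.2% three-value case the chi-squared levels are at or below nominal, within simulation error. Nor is 20-24 lesions the planned enrolment; it is what remains after the loss that the plan itself reports. When very few lesions move, the limit is the number of events, and ordering the test gains nothing.

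**What to change.** In section 13.1:
1. State the change categories and reconcile them with section 10.0.
2. Replace the cluster-adjusted chi-squared test with a child-level permutation test. The statistic is the between-arm variation in mean lesion ICCMS change. Shuffle arm labels over children within randomisation blocks and compare the p-value with 0.025. A cluster-adjusted mean-score test is an alternative, but it held its level less well in the simulations when few lesions changed.
3. If the outcome is reduced to progressed / not progressed, apply the same permutation to the 3 × 2 table.
4. Do not fit the Poisson or negative binomial log-link GEE to the signed change. Use an identity-link Gaussian or an ordinal GEE for the score, or keep the Poisson model for a binary progression outcome only.

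The cost is SAP wording and a few lines of code. No new data or patients are needed.

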6.0 STRATIFICATION/DESCRIPTIVE FACTORS/RANDOMIZATION SCHEME

- 6.1 We have not defined any *a priori* stratification factors.
- 6.2 Descriptive factors: Age, Gender, Race,, Date of Initial exam, Date of Recall exam/Followup, , Number of posterior caries on primary teeth that qualify for this present study, DMFS, Which interproximal surface (mesial or distal), Which primary molar, and Radiographic depth of Lesion based on ICCMS Categories (see Table 1 in Appendix).
- 6.3 Once participants have met eligibility criteria and have undergone the informed consent process (parental permission and assent, if applicable), they will be randomized to one of the three treatments 1:1:1 using a cluster-randomized design. That is, participants, not teeth, will be randomized, though multiple teeth per participant may be treated. Using the uniform distribution, the statistician will generate a random number sequence. We will use blocked randomization (blocks of six) to better ensure an even distribution across groups. Once group

Version date: 07/31/22

assignments have been made, the statistician will prepare numbered, opaque envelopes containing the random study arm assignments, which the investigators will use sequentially, as study participants accrue (i.e., the study identification number will match the number on the envelope).

7.0 STUDY AGENT ADMINISTRATION OR INTERVENTION AND TOXICITY MANAGEMENT PLAN

- 7.1 Treatment protocol after patients are randomized into one of three treatment groups:
 - 7.1.1 Fluoride varnish application (Control Group 1): Bulk saliva removed with saliva ejector. All teeth wiped dry with cotton gauze. One unit dose (0.4 ml) of fluoride varnish will be applied to all dentition then interproximal surfaces of all teeth will be flossed.
 - Professionally applied fluoride varnish has been shown to inhibit demineralization and enhance remineralization in early enamel caries.²² Current Caries Risk Assessment (CRA) protocol indicates fluoride varnish applications at 3-6 months intervals for high caries risk patients.^{4,5}

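### The stated 80% power fits a two-arm difference in means; the plan gives no power for the three-arm chi-squared test it lists first

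*Combined protocol and SAP*

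**What the plan says.** Section 6.3 sets up three arms with children as the unit of allocation: "they will be randomized to one of the three treatments 1:1:1 using a cluster-randomized design". In Section 13.1 group 1 is fluoride varnish alone, group 2 is SDF with Super Floss plus varnish, and group 3 is SDF without Super Floss plus varnish. The expected result is given as a ranking only: "We hypothesize that group 2 will have the best outcomes", with second place given by the words "followed by group 3".

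The order of analysis is also in Section 13.1: "First we will evaluate the association between treatment groups and the change in ICCMS score from baseline at 6 and 12 months". The method named for this step is given as "using a cluster-adjusted chi-squared test". GEE with a Poisson or negative binomial family and a log link follows. The outcome categories and degrees of freedom of the chi-squared test are not given, and no pair of arms is named as the primary comparison.

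The Power Analysis assumes "a clinically significant mean difference of 0.2", an SD of 0.2, the mean of an ICC range of 0.0 to 0.25, two lesions per child, a cluster-size variation term of 0.65, and "a two-sided adjusted Type I error rate of 0.025". It concludes: "we will have 80% power with 11-12 participants per group". It does not say which arms differ by 0.2 or which test is powered.

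**The concern.** A power figure belongs to a particular test of a particular alternative. A single mean difference with a single SD describes a contrast between two arms. A test of association across three arms spreads its sensitivity over at least two dimensions. It therefore needs a larger noncentrality for the same power, and more again if the outcome has several unordered categories.

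Section 13.1 justifies raising enrolment from 39 to 60 by the need for sufficient power. If the first reported result is a non-significant three-arm test, there is a risk that it is read against an 80% figure that was not derived for it.

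**Working it through.** **Inputs.** From the Power Analysis: difference 0.2, SD 0.2, two-sided alpha 0.025, m = 2 lesions per child, ICC = (0.0 + 0.25)/2 = 0.125. The 0.65 is called a covariance of cluster sizes; I read it as the coefficient of variation (CV). Three arms come from Section 6.3.

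**Step 1: reproduce the stated figure as a two-arm comparison of means (normal approximation).**

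- Lesions per arm before clustering: 2 × (2.2414 + 0.8416)² × (0.2/0.2)² = 19.01.
- Design effect: 1 + [(1 + 0.65²) × 2 − 1] × 0.125 = 1 + 1.845 × 0.125 = 1.2306.
- Lesions per arm: 19.01 × 1.2306 = 23.4, or 11.7 children (10.7 without the CV term).
- Effective lesions per arm: 11 × 2/1.2306 = 17.88 and 12 × 2/1.2306 = 19.50.
- Power = Φ(√(n_eff/2) − 2.2414): Φ(2.990 − 2.241) = 77.3% at 11 and Φ(3.123 − 2.241) = 81.1% at 12.

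This matches the plan's 80% at 11-12 per group.

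**Step 2: a three-arm, 2-df test with the same inputs.** Noncentrality λ = n_eff × Σ(μᵢ − μ̄)²/SD². The critical value is 7.38 (chi-squared, 2 df, alpha 0.025). The arm means are my assumptions, because the plan gives none.

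| Assumed means, worst to best arm | Σ(μᵢ − μ̄)²/SD² | λ at 11; 12 per arm | Power at 11; 12 |
|---|---|---|---|
| 0, 0.1, 0.2 (midway) | 0.500 | 8.94; 9.75 | 67.5%; 72.0% |
| 0, 0.15, 0.2 | 0.542 | 9.68; 10.56 | 71.6%; 76.0% |
| 0, 0, 0.2 or 0, 0.2, 0.2 (tied) | 0.667 | 11.92; 13.00 | 81.7%; 85.4% |
| 0, 0.2, 0.4 (0.2 per step) | 2.000 | 35.75; 39.00 | above 99% |

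In the midway case λ equals that of the two-arm test (2.990² = 8.94; 3.123² = 9.75). The whole loss of 9 to 10 points therefore comes from the second degree of freedom.

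**Step 3: sensitivity of the midway case at 11 and 12 per arm.**

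- F reference on cluster degrees of freedom: 61.0% and 66.1%. On the same basis the two-arm test has 71.2% and 75.8%, so the gap is again about 10 points.
- Four degrees of freedom at the same λ, as a table of three outcome categories would have (Section 10.0 speaks of lesions remineralizing, arresting or progressing): 55.3% and 60.1%.
- ICC 0: 77.9% and 82.0%. ICC 0.25: 58.5% and 63.0%.

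A test on means is only a proxy for a chi-squared test on a table of change categories. The categories would have to be specified before its power could be calculated directly.

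**The case against.** A reader might infer that the first planned test has only about 61-72% power under the ordering the plan expects. The documents do not support that. They give ranks, not distances. The range needs 0.2 to be the full best-to-worst spread and group 3 to lie exactly midway, which is the least favourable spacing for that spread. With group 3 nine-tenths of the way to one end, 2-df power is already 77.3-81.3%. The 61% also comes from an F reference, so setting it against a normal-approximation 80% roughly doubles the apparent loss.

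It can also be said that the two-arm reading is itself an inference, since the power paragraph names no test. A three-arm calculation with two arms tied also lands near 80% (81.7% at 11 per arm with a chi-squared reference; 80.4% at 12 with an F reference). That is fair, but the plan states no arm means and expects group 3 to come second, so nothing in it points to that reading.

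Finally, listing the chi-squared test first sets a sequence and does not make it decisive, and the plan calls the trial a pilot. That a null result would be misread is a risk, not something the documents show. Power after the roughly 48% loss to follow-up is a separate matter, because attrition lowers the two-arm figure as well.

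What stands is the mismatch: no power is stated for the three-arm test, and no powered contrast is named.

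**Conclusion.** The point holds as a mismatch between the powered comparison and the first planned test. The 80% at 11-12 per group is reproduced by a two-arm difference in means and is not a property of the three-arm chi-squared test.

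The size of the gap depends on assumptions. Like for like, the midway 2-df scenario gives about 68-72% against 77-81% for two arms, or 61-66% against 71-76% with an F reference. Four degrees of freedom would lower it to about 55-60%. If group 3 ties with an end arm, 2-df power is about 82-85% and there is no shortfall. All these figures take ICC 0.125, the 0.65 as a coefficient of variation, and 11-12 evaluable children per arm.

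It would also be wrong to infer that the calculation already covers group 2 versus group 1 in the planned GEE. The plan names no pair of arms, and a log-link count model estimates a ratio, not a difference in means with SD 0.2.

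**What to change.** Name one two-arm contrast at 12 months, for example group 2 versus group 1, as the primary test, and make the three-arm chi-squared test supportive. Then do one of two things:

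- analyse that contrast as a cluster-adjusted difference in mean ICCMS change, which is what the calculation describes; or
- keep the GEE model and recompute power for the contrast under that model.

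If the three-arm test is to stay first, replace the 80% with its power for stated arm values, outcome categories and degrees of freedom. About 68-72% can be shown there, labelled as the scenario with group 3 midway and 2 df.

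The cost is SAP wording, a short recalculation and possibly a less favourable stated figure. No extra patients are required.

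### Section 13 fits a log-link Poisson or negative binomial GEE to a signed change in ICCMS category with no stated recoding, and its confounder rule names an odds ratio that this model does not estimate

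*Combined protocol and SAP*

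**What the plan says.** Section 13 defines the endpoint as a change: "The primary outcome is the change in ICCMS category, as assessed by radiographic evidence, from baseline to 12 months". Section 13.1 says that a higher score means progression, and that the intervention arm should do best "as measured by no change or reversal in ICCMS classification indicating no caries progression or remineralization".

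Two simpler steps come first. One is "We will calculate the median difference at each time point and use an individual-level model", with a cluster-adjusted standard error. The other is "First we will evaluate the association between treatment groups and the change in ICCMS score from baseline at 6 and 12 months", by a cluster-adjusted chi-squared test. The plan then takes the same pair of variables, treatment group and change in score, into a GEE, "specifying a Poisson (or negative binomial, if overdispersed) family and a log link". It adds: "We will also specify an exchangeable correlation matrix and a robust standard error". Confounders are variables "which alter the odds ratio by >15% when included in the model".

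Three other places bear on this:
- Section 10 words the primary outcome as arrest, meaning that no shift in classification shows progression.
- Section 5.3.2 withdraws a tooth that goes beyond category 3, while section 13 calls for an intent-to-treat primary analysis.
- The Power Analysis works with a mean difference.

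**The concern.** A change score here can be negative, zero or positive, and the good results are the zeros and negatives. Poisson and negative binomial distributions are for counts of zero or more, and a log link needs a positive mean. Read literally, the model loses its estimate most readily when an arm does well, which is what the trial hopes to show.

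This GEE is the only regression in the plan with a stated family and link, so it is the planned source of a model-based treatment effect. If it fails, or if its outcome coding has to be guessed, the coding or the model will be chosen after the outcomes have been seen.

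**Working it through.** **1. Children per arm.** The plan's own figure reproduces. I read its covariance of cluster sizes as a coefficient of variation and take the ICC at the midpoint, 0.125.
- Lesions per arm before clustering: 2 × (2.2414 + 0.8416)² × (0.2/0.2)² = 19.01.
- Design effect: 1 + [(0.65² + 1) × 2 − 1] × 0.125 = 1.2306.
- Children: 19.01 × 1.2306 / 2 = 11.70, in line with the stated 11-12 per group.

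The plan also reports that "10% loss to follow up has increased dramatically to ~48"%. With 60 recruited, 60 × (1 − 0.48) / 3 = 10.4 children per arm remain. I therefore use 12 and 10.

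**2. What the model estimates.** With arm indicators only, a log link and equal lesion counts per child, the GEE solution for each arm is log(arm mean change). The treatment effect is log(mean₁/mean₀). If either mean is zero or less, no finite value exists. This is algebra and does not depend on software.

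With uneven lesion counts, an exchangeable correlation ρ weights each lesion by 1/[1 + (m − 1)ρ], where m is the child's number of lesions. The weighted mean can then be zero or negative although the plain mean is positive.

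**3. Constructed example (my data, 24 lesions per arm, in pairs).** The control arm has 8 lesions at +1, 14 at 0 and 2 at −1, so its mean is (8 − 2)/24 = 0.25.

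| Comparison arm (+1/0/−1) | Mean | Poisson on signed change | Mean difference | Risk ratio for progression | Odds ratio for progression |
|---|---|---|---|---|---|
| 5/16/3 | 0.083 | ratio 0.33 | −0.167 | 5/8 = 0.625 | 0.526 |
| 3/18/3 | 0 | coefficient −37.9, SE about 9 × 10¹⁵ | −0.25 | 3/8 = 0.375 | 0.286 |
| 2/16/6 | −0.167 | fit fails | −0.417 | 2/8 = 0.25 | 0.182 |

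The negative binomial fit failed in all three rows, including the first, where both means are positive. The last two columns show that an odds ratio is not what a log link returns.

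Adding a constant to remove the negatives does not help, because the ratio then depends on the constant. For means 0.083 and 0.25 it is 0.33 with no shift, 0.87 with +1 and 0.95 with +3.

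**4. Simulated datasets (statsmodels).**
- Poisson, equal lesion counts: no finite estimate in 762 of 762 datasets with an arm mean of zero or less, and in 0 of 1,638 others.
- Poisson, uneven counts, all arm means positive: failed in 9 of 208 datasets in one check and 5 of 127 in another.
- Negative binomial, all arm means positive: failed in 202 of 208 and 123 of 127. In the constructed example the error arose when the deviance was evaluated, so other software may behave differently. Stata 15, the plan's software, was not tested.

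**5. Chance that one arm's mean change is zero or less.** All rates are assumed. There are 2 lesions per child, a latent correlation of 0.2 (score ICC 0.11-0.15) and 60,000 simulated arms per case.

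| Progressed/unchanged/reversed, % | 12 children | 10 children |
|---|---|---|
| 40/55/5 | 0.4% | 0.9% |
| 25/70/5 | 5% | 7% |
| 15/80/5 | 20% | 23% |
| 10/85/5 | 37% | 40% |
| 10/80/10 | 59% | 60% |

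Hand check with a design effect of 1.13 and a continuity correction of 0.5/24 = 0.021:
- 25/70/5: mean 0.20, variance 0.25 + 0.05 − 0.04 = 0.26, SE √(0.26 × 1.13/24) = 0.111, z = (0.021 − 0.20)/0.111 = −1.62, about 5%.
- 10/85/5: mean 0.05, variance 0.15 − 0.0025 = 0.1475, SE 0.083, z = −0.35, about 36%.

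**6. Standard errors for the alternatives.** Type I error against nominal 0.025, one assumed null (25/70/5 in every arm), 4,000 datasets per case, among those fitted. The four values are 10 and 12 children with equal lesion counts, then 10 and 12 with uneven counts.
- Gaussian identity link, ordinary robust SE: 0.044, 0.039, 0.064, 0.059.
- Gaussian identity link, Mancl-DeRouen SE with t reference: 0.021, 0.022, 0.024, 0.030.
- Binary Poisson, ordinary robust SE: 0.008, 0.016, 0.027, 0.029.
- Binary Poisson, Mancl-DeRouen SE with t reference: 0.0005, 0.0025, 0.0055, 0.0067.

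**The case against.** The strongest defence is that the sponsor means a binary outcome. Section 10 defines arrest as the absence of progression, a chi-squared test suits categories, and an odds ratio belongs with a yes/no variable. For a 0/1 outcome, a log-link Poisson GEE with robust standard error is a sound way to obtain a risk ratio. The intent may well be this, and the problem is then largely one of specification. But section 13 never says so. It defines the outcome as a change and carries that change into the GEE. A negative binomial option does not fit a 0/1 variable, and the Power Analysis uses a mean difference. Even on the binary reading, the confounder rule still names the wrong measure.

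Second, the GEE only follows up a chi-squared test. That stands. A reader might infer that the trial has no workable primary analysis, but the documents do not support this: the chi-squared test and the median difference both run on signed changes.

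Third, the failure rates depend on assumption and run from 0.4% to 60%. That also stands. The direction is firm; the size is not.

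Fourth, withdrawn teeth. A reader might infer that lesions passing category 3 drop out of the analysis, so that a lesion starting at category 3 could never count as progressed. Section 5.3.2 speaks of withdrawal from the study and gives no scoring rule. Given intent-to-treat, and given that the radiograph has already recorded the event, exclusion is the less natural reading. One sentence in the plan would settle it.

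**Conclusion.** The regression as written does not match its outcome and should be corrected before outcomes are analysed by arm. That conclusion rests on the plan's text and on algebra. The confounder rule is wrong on either reading of the outcome.

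The size rests on assumed rates: with 12 children per arm, the chance of an arm mean of zero or less is about 5% at 25/70/5 and 37% at 10/85/5, and it rises as an arm improves.

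Two stronger readings go too far. One is that the model fails exactly when an arm mean is zero or less. That is exact only for Poisson with equal lesion counts; uneven counts and the negative binomial option can fail with positive means, and the software evidence is from statsmodels alone. The other is that this point undermines the sample size. The stated 11-12 per group comes from a two-mean formula that does not use the GEE.

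**What to change.** Before outcomes are analysed by arm, reconcile sections 10 and 13 to one primary outcome at 12 months, and match the GEE to it.

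- **(a) If change in category:** use a Gaussian identity-link GEE and report a mean difference. Use a small-sample-corrected robust standard error (for example Mancl-DeRouen) with a t reference, because the ordinary one gave type I error of 0.039-0.064 against 0.025 under the assumed null.
- **(b) If binary progression:** keep the log-link Poisson GEE with the plan's robust standard error, drop the negative binomial option, report a risk ratio, and state what is reported if an arm has no progression. The simulation gives no reason to add the small-sample correction here; with it, type I error fell to 0.0005-0.0067.

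In both cases, count a tooth whose radiograph shows progression beyond category 3 as progressed in the analysis, although it is then withdrawn under section 5.3.2. Replace the odds ratio in the confounder rule with the model's own effect measure.

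The cost is a text amendment to sections 10 and 13, with no new variables. Date it, state whether the 6-month interim analysis has been done, and under (a) check that the named software provides the corrected standard error.

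Each option has a price. Option (a) treats category steps as equal, and its exchangeable fit failed in 46 to 104 of 4,000 datasets with uneven lesion counts (about 1-3%). Option (b) pools reversal with no change and may give no estimate if an arm has no progression; in simulation it gave none in 24 to 184 of 4,000 datasets (0.6-4.6%), even with 25% progression in every arm.
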